## 9.2 Safety

Routine safety and tolerability will be evaluated from the results of reported signs and symptoms, scheduled physical examinations, vital sign measurements, and clinical laboratory test results. More frequent safety evaluations may be performed if clinically indicated or at the discretion of the investigator.

### **Physical Examination**

Complete and symptom-directed physical examinations will be performed by a licensed physician (or physician's assistant or nurse practitioner).

### **Vital Signs**

Vital signs (blood pressure, respiratory rate, pulse rate and temperature) will be obtained in the sitting position. Patients should be sitting for 3-5 minutes prior to obtaining vital signs.

### **Safety Laboratory Determinations**

Laboratory evaluations will be performed as noted in the flow chart.

## **10 STATISTICAL CONSIDERATIONS**

### **10.1 Sample size determination**

This is an open-label phase II study of systems biology guided therapy for breast cancer patients positive for Oestrogen receptor after Aromatase inhibitor and CDK inhibition. Based on the SOLAR-1 trial, 25% of tumors would have PIK3CA mutation, so 25% of people would be treated with fulvestrant plus alpelisib with a median PFS in that group of 11 months and 75% of people would be treated with fulvestrant with a median PFS in that group of 6 months.(3) The weighted average of these medians is 7.25 months, but since the actual distributions of the progression free survivals are not available, we will use a conservative estimate of the expected median PFS of the historical control group (fulvestrant +/- alpelisib as second line unguided therapy) of 8 months.

Based on the preclinical assessments and assay features, it is expected that 10% of patients enrolled in the trial will be assigned to capecitabine, 25% to fulvestrant/alpelisib, 32.5% to fulvestrant, and 32.5% to exemestane everolimus. The goal is to assign people to therapy so that the capecitabine group will have a median PFS of 18 months (75th percentile of survival in BOLERO-6(5)), the fulvestrant group will have a median PFS of 10 months (75th percentile of survival in SOLAR-1(3)), and the exemestane/everolimus group will have a median PFS of 13 months (25th percentile of BOLERO-2(6)). From the results of the BOLERO-2 trial, BOLERO-6 trial, and the SOLAR-1 trial, it is hypothesized that the weighted median PFS with genomic- guided therapy will be improved to 12.1 months from 9 months of fulvestrant +/- alpelisib as second line unguided therapy after AI+CDK inhibitor.

With an alpha of 0.1, beta of 0.2, 18 months of accrual, and 6 months of follow-up, 66 patients are needed to detect a 4-month improvement in the median PFS (from 8 months to 12 months) with genomic- guided therapy, assuming an exponential distribution using a 2-sided Log-rank test. Accounting for 10% loss, the trial will enroll 74 eligible patients.

## 10.2 Statistical Analysis

### 10.2.1 Primary Endpoint

#### **Progression Free Survival (PFS)**

PFS is defined as the time from the time results are given to the treating oncologist to the first occurrence of disease progression or death from any cause (whichever occurs first) according to RECIST 1.1. Patients without disease progression or death at the time of analysis will be censored at the last disease assessment date from their last evaluable RECIST v1.1 assessment.

For the primary objective, all enrolled patients who receive therapy concordant with the genomic recommendation will be evaluable for analysis. Concordant therapy will be any anti-estrogen plus any PI3K inhibitor in the “fulvestrant plus alpelisib” group, any anti-estrogen plus any MTOR inhibitor in the “exemestane plus everolimus” group, any antiestrogen in the “fulvestrant” group, and any cytotoxic chemotherapy in the “capecitabine” group.

The PFS curve will be estimated using the Kaplan-Meier product-limit method. Two-sided, 95% CI for the median PFS will be computed by the Brookmeyer and Crowley method with log-log transformation.

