**Name of Institution**

## STUDY SUMMARY

Title	Systems Biology Guided Therapy for Breast Cancer Positive for Oestrogen Receptor after Aromatase Inhibitor and CDK inhibition.
Short Title	SPOCK
Protocol Identifiers (IRB – internal)	U21-02-4401
IND number	N/A
Phase	II
Design	
Open label, interventional
 
All patients will have a biopsy at the beginning of the trial. The biopsy will be sent for DNA sequencing through FoundationOne (clinical test) and RNA profiling at Fulgent (research test) for determination of activation of various oncogenic pathways and phenotypes. The results will be analyzed by [name] and [name], and a treatment recommendation will be made to the treating physician based on the algorithm below.
 
Biopsies will also be performed 2-4 weeks after the start of therapy for correlative purposes.

Study Duration	24 months recruitment, with up to 3 years of follow up per patient
Objectives	
Primary To determine if systems biology guided therapy can improve PFS
 
Secondary To determine the minimum turn-around time needed for systems biology analysis
 
To determine the response rate to systems biology guided therapy
 
To compare PFS based on concordance with recommended treatment

Number of Subjects	74 treated according to recommendations
Diagnosis and Main Eligibility Criteria	
 
• Metastatic or incurable breast cancer
 
• Progression while on aromatase inhibitor and CDK inhibitor
 

	
 
• Biopsiable lesion
 
• ECOG 0-2
 
• Age 18 or greater
 

Study Product, Dose, Route, Regimen	Drug determined by treating oncologist based on recommendation from systems biology analysis.
Duration of administration	Until intolerance or progression.
Reference therapy	Unguided therapy
Statistical Methodology	The PFS will be compared to 8 months, which is the approximate expected median PFS of fulvestrant +/- alpelisib as second line unguided therapy after AI+CDK inhibitor based on SOLAR-1. With a two-sided alpha of 0.1, beta of 0.2, 18 months of accrual, and 6 months of follow-up, 74 patients are needed to detect a 4 month improvement in PFS with genomic - guided therapy.

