#### 1.1.2 Primary Endpoint

Progression free survival in patients treated in concordance with recommendation

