#### **4.2 Number of Patients**

66 evaluable patients, 74 total to account for dropout

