## 6 TREATMENT PLAN

### 6.1 Patient enrollment

Once a patient signs the informed consent form, she/he may be screened. If all inclusion/exclusion criteria are met, then they are enrolled. During screening a biopsy site will be identified. In accordance with the ASCO Ethical Framework for Mandatory Research Biopsies, because the biopsy results are used in the primary endpoint of the study, the biopsy risk may be low or moderate risk (expected rate of major complications < 1.5%), including biopsy of bone marrow, skin, superficial masses, intra-abdominal masses, peripheral thoracic masses that can be accessed without penetrating lung, or sites that will be biopsied for other clinical purposes.

Note that after patients may be continued on the most recent therapy up to the biopsy at the discretion of the treating oncologist. After the biopsy, the treating oncologist may opt to start a new therapy while waiting for results and then switch based on results if desired. No wash-out period necessary.

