## 8 STUDY CALENDAR

### MONTHLY Calendar

Examination	Pre-study  (≤ 28 days of signed consent)	After registration	4-8 weeks after start of therapy 	Every 3 months (+/- 1 month) 	M9D1 (+/- 1 month)	EOT 
Informed consent	X					
Medical history	X					
Eligibility criteria	X					
Vital signs	X	X				
Physical examination	X					X
Study blood tube 		X	X 		X	X
CBC	X					
PT/INR	X					
Biopsy		X	X 			X 
Restaging Scans				X 		X

1 ALL Pre-study/Screening procedures should be completed within 4 weeks of study enrollment - with the exception of laboratory tests which need to be completed within 2 weeks prior to study enrollment.

2 Study blood tube: One lavender top 10 ml tube and one red/gray top 8.5ml tube

3 End of treatment biopsy is optional

4. Restaging scans are recommended to include a chest/abdomen/pelvis CT and either bone scan or PET scan at least every 3 month (+/- 1 month). MRI is an acceptable substitute for CT. After 15 months they can be done at a frequency of the prescriber's discretion.

5. Week 6 blood and biopsy can be done at least 4 weeks and no more than 8 weeks after start of therapy. Start of therapy is defined as the first day of drug taken by the patient after delivery of the biopsy report to the treating oncologist.

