#### 9.1.3 Progression Free Survival

Progression free survival will be determined from the day the biopsy result report is given to the treating oncologist until the date of progression or death, whichever comes first, by RECIST 1.1.

Patients who have not progressed or died at the time of analysis will be censored at the time of the latest date of assessment from their last evaluable RECIST v1.1 assessment.

For the primary analysis, patients who change therapy for reasons other than RECIST 1.1 progression will be censored at the time of starting new therapy, but a sensitivity analysis will be performed counting these as progression events. Patients who continue on therapy at the discretion of the treating oncologist but who have progression by RECIST 1.1 will be considered to have progressed and will have end of treatment (EOT) procedures done.

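### PFS is timed from report delivery, but only patients who later receive concordant therapy are analysed; early failures can drop out of the primary set and no analysis shows the effect

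*Combined protocol and SAP*

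**What the plan says.** - **Time origin.** Section 9.1.3: "Progression free survival will be determined from the day the biopsy result report is given to the treating oncologist". Section 10.2.1 uses the same origin.
- **Analysis set.** Section 1.1.2 defines the endpoint as "Progression free survival in patients treated in concordance with recommendation", and section 10.2.1 states that "all enrolled patients who receive therapy concordant with the genomic recommendation will be evaluable for analysis".
- **Start of therapy.** Section 8, note 5: "Start of therapy is defined as the first day of drug taken by the patient after delivery of the biopsy report". No maximum interval is given. Under section 6.1 the oncologist may "start a new therapy while waiting for results and then switch based on results if desired".
- **Benchmark.** Study Summary: "The PFS will be compared to 8 months". The trial has a single arm (section 4.1).
- **Numbers.** Section 4.2: "66 evaluable patients, 74 total to account for dropout".
- **Other PFS analyses.** Section 9.1.3 has one sensitivity analysis, which counts changes of therapy without RECIST progression as events. Section 10.2.2 compares concordant with discordant patients by an ordinary log-rank test on the same PFS definition. No all-patient, landmark or delayed-entry analysis is stated.

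**The concern.** Membership of the primary set is decided after time zero. A patient who fails between the report and the recommended drug, and never takes it, is removed. A patient who stays event-free can still qualify. This is immortal-time bias, and in a single-arm trial no control group shares the exclusion. Removing early failures can only raise observed PFS, even if guidance does nothing.

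The problem does not reach every patient. Someone already on a concordant bridging drug has no gap, and someone who progresses and still starts concordant therapy stays in with an early event. Separately, the oncologist's discretion adds selection that could act in either direction.

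The concordance comparison in section 10.2.2 has the same fault: a patient who fails early and is then given something else counts against the discordant group. A spurious difference would look like support for the trial's hypothesis.

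**Working it through.** **1. The plan's sample size.** Inputs from section 10.1: medians 8 and 12 months, two-sided alpha 0.10, power 0.80, 18 months of accrual plus 6 of follow-up, exponential PFS.

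- Event probability at median 12, with λ = ln 2/12: 1 − (e^(−6λ) − e^(−24λ))/(18λ) = 0.560.
- Events: (1.645 + 0.842)²/(ln 1.5)² = 37.6. Patients: 37.6/0.560 = 67.1. A hazard-difference version gives 66.4. The plan says 66.
- With 10% loss: 66/0.9 = 73.3, so 74, as stated.

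The arithmetic is sound. The issue is the analysis set.

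**2. Size of the mechanism.** The documents give no gap, so take 1 month as an assumption. At a true median of 8, the share failing in the gap is g = 1 − 2^(−1/8) = 0.083, or 74 × 0.083 = 6.1 patients. If a share e of these is excluded, the apparent median is 8 × [1 − log₂(1 − e·g)]: 8.10, 8.24, 8.49 and 9.00 months for e = 10%, 25%, 50% and 100%.

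**3. Error of the primary comparison.** Section 10.2.1 names no test. I assume a one-sample log-rank: Z = (O − E)/√E, where O is observed events and E = (ln 2/8) × total follow-up time, with success if Z < −1.645. Nominal error in this tail is 5%. Simulation: n = 66 analysed, 40,000 runs.

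| Gap, true median | 0% excluded | 10% | 25% | 50% | 100% |
|---|---|---|---|---|---|
| 1 month, all patients, median 8 | 4.3% | 4.9% | 6.0% | 8.8% | 17.1% |
| 1 month, half of patients, median 8 | 4.1% | 4.5% | 5.2% | 6.3% | 8.6% |
| 0.5 month, all, median 8 | 4.2% | 4.7% | 5.2% | 6.3% | 8.8% |
| 0.25 month, all, median 8 | 4.3% | 4.4% | 4.6% | 5.1% | 6.2% |
| 1 month, all, median 7.25 | 0.8% | 1.0% | 1.3% | 2.0% | 5.2% |

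The 7.25 months is section 10.1's own weighted figure: 0.25 × 11 + 0.75 × 6.

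If success instead means that the 95% CI for the median lies above 8 (8,000 runs, 1-month gap, true median 8), the error is 2.0%, 2.6%, 2.9%, 4.6% and 8.7% across the same exclusion shares.

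**4. Using the 8 non-evaluable patients of section 4.2.** Suppose k of the 8 are 1-month gap failures and the rest are random. For k = 0, 1, 2 and 4 the error is 4.2%, 5.5%, 7.2% and 10.8% at median 8, and 0.8%, 1.1%, 1.5% and 2.7% at median 7.25.

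**5. The concordance log-rank test.** N = 74, all medians 8 (no true difference), two-sided 5% assumed, 1-month gap, 10,000 runs.

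| Scenario | 10% discordant by choice | 20% | 30% |
|---|---|---|---|
| No reclassification | 6.5% | 5.5% | 5.2% |
| 25% of gap events classed discordant, gap for all | 16.0% | 9.7% | 7.6% |
| Same, gap for half | 10.7% | 7.2% | 6.2% |
| Gap for all, half of those reclassified die untreated and join neither group | 11.5% | 7.4% | 6.3% |
| With a 28-day landmark | 6.4% | 5.9% | 5.5% |

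Nearly all the excess favours concordance. In a repeat run of the second row, with totals of 16.3%, 9.7% and 7.2%, the share favouring concordance was 15.8%, 9.0% and 6.3%.

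**6. Do the remedies work?** With full exclusion and gaps of 0.5, 1 and 1.5 months, delayed entry gives primary errors of 4.4%, 4.2% and 4.1%. A 28-day landmark against 8 months gives 4.2%; this relies on the exponential assumption, under which the residual median is still 8.

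**The case against.** The case for calling this minor is substantial.

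- **Stated method.** Section 10.2.1 gives only a Kaplan-Meier curve and a 95% CI for the median. Judged by that CI, error moves from 2.0% to at most 2.9% for 10-25% exclusion. This stands.
- **Conservative benchmark.** At a true unguided median of 7.25 months there is no material inflation. This stands.
- **Scan timing.** Section 8, note 4 recommends scans about every 3 months, so few RECIST events can be recorded in a 1-month gap. If scans were timed from the report and 90% of events were found at them (an assumption), about 6.1 × 0.10 = 0.6 of the 6.1 gap events would remain. This favours the low end of the tables.
- **Follow-up.** With the 24 months of recruitment and up to 3 years of follow-up in section 4.4, error at median 8 is 5.6% at 25% exclusion and 13.8% at full exclusion, somewhat lower than above.
- **The 8 patients.** Sections 4.2 and 10.1 attribute them to dropout or loss, and the Study Summary gives 74 as the number treated according to recommendations. Four gap failures among the 8 would mean about two-thirds (4 of 6.1) never received concordant therapy. That calculation is illustrative only.
- **Visibility.** Section 10.2.2 already requires PFS in discordantly treated patients, so those failures would be seen. However, they appear only as a comparison group, and patients who receive no therapy appear nowhere.

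These points limit the size. They do not remove the bias or show which scenario occurred. The section 9.1.3 sensitivity analysis recodes changes of therapy and brings back no excluded patient.

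**Conclusion.** The concern holds and should be fixed before analysis. As written, the plan selects the primary set on something that happens after the clock starts, and any early failures lost this way favour guidance.

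For the primary result the effect is probably small. Error is about 5-6% against a nominal 5% if 10-25% of 1-month gap events are excluded, near nominal for a gap of about a week, and 17% only at the extreme of full exclusion. At a true median of 7.25 it does not materially exceed nominal. The concordance log-rank test is more exposed, at about 8-16% against 5-7% when a quarter of gap events are classed as discordant and all patients have the gap, or about 6-11% when only half do.

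Confidence in the size is medium. The gap, the share excluded, the primary test and the secondary alpha are all assumptions. The direction of the immortal-time part is not in doubt; the direction of discretionary selection is.

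**What to change.** 1. Keep the concordant-only primary endpoint. Pre-specify beside it the same comparison with 8 months in all patients whose report was delivered, from the report date, whatever therapy followed. Treat this as a supporting estimate, not a success gate, and describe the primary result as PFS in concordantly treated patients.
2. For the section 10.2.2 log-rank test, and as a sensitivity analysis of the primary result, classify patients at a landmark fixed in advance (for example 28 days after the report), start the clock there and leave out earlier events. Delayed entry at the first concordant dose is an alternative. Either removes the immortal-time part only, not selection.

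**Cost.** SAP wording and extra analyses. Section 6.3 already records report dates and PFS follow-up, and section 10.2.2 already needs PFS in discordant patients. The primary endpoint, sample size and success criterion do not change.

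**Downsides.** The all-patient estimate is diluted. With 74 patients and a concordant median of 12, its power at 90%, 80% and 70% concordance is about 0.79, 0.70 and 0.60 if discordant patients have a median of 8, and 0.69, 0.47 and 0.26 if 5. It should be read as an estimate with its CI. A 28-day landmark drops about 4 to 6 of 74 patients and lowers power from about 0.86 to 0.82.

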### 10.2.2 Secondary Endpoints

#### **Turn-around time needed for systems biology analysis**

The turn-around time is defined as time from when patient's biopsy sample is shipped until the time when the report is sent. The turn-around time will be summarized by the range, mean, median, and STD.

#### **Objective Response Rate (ORR)**

The ORR is defined as the proportion of participants who achieve either a complete response or PR, as defined by BICR using RECIST v1.1. The ORR will be estimated and its 2-sided 95% CIs will be calculated using the Clopper-Pearson exact method.

#### **PFS**

As defined previously. Log-rank test will be used to compare the PFS of patients who receive the treatment recommended by the genomic analysis with those who are given a different treatment.

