### 1.2 Secondary Objectives

To determine the minimum turn-around time needed for systems biology analysis

To determine the response rate to systems biology guided therapy

To compare PFS based on concordance with recommended treatment

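### The secondary concordant-versus-discordant PFS test sets groups by treatment received after the clock starts and is unadjusted, so it can favour concordance with no treatment effect

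*Combined protocol and SAP*

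**What the plan says.** All references are to the combined protocol and SAP.

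- **Objective.** Section 1.2 lists as a secondary objective: "To compare PFS based on concordance with recommended treatment".
- **Test.** Section 10.2.2 (PFS): "Log-rank test will be used to compare the PFS of patients who receive the treatment recommended by the genomic analysis". The comparator is likewise defined by what the patient was actually given, not by what was planned. The section names no covariates, strata, landmark or time-dependent exposure, and gives no alpha or expected group sizes.
- **Time zero.** Section 9.1.3: "Progression free survival will be determined from the day the biopsy result report is given to the treating oncologist". Section 10.2.1 agrees.
- **Group label.** Section 10.2.1 defines concordance by receipt, for the primary analysis: "all enrolled patients who receive therapy concordant with the genomic recommendation will be evaluable for analysis". No deadline for starting the drug is given.
- **When treatment starts.** Section 8, footnote 5: "Start of therapy is defined as the first day of drug taken by the patient after delivery of the biopsy report". This is on or after time zero.
- **Bridging.** Section 6.1: "the treating oncologist may opt to start a new therapy while waiting for results and then switch based on results if desired". No time limit is set on the switch.
- **Who chooses.** Study Summary: "Drug determined by treating oncologist based on recommendation from systems biology analysis". Allocation is not randomised.

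**The concern.** The clock starts before the group is known. To be labelled concordant, a patient must still be event-free when the recommended drug begins. A patient who progresses or dies on a non-matching bridging drug has, on a natural reading of section 10.2.2, been given a different treatment. Those early events then count against the discordant group, while the concordant group is credited with guaranteed event-free time (immortal time bias).

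There is a second, separate problem. The oncologist decides whether to follow the recommendation, so the groups may differ in prognosis, and a plain log-rank test ignores that. The mix of recommendations may differ too. Section 10.2.1 makes concordance easier in the fulvestrant group, where any antiestrogen qualifies, than in groups that need an added inhibitor or chemotherapy. Section 10.1 targets different medians by group (10, 13 and 18 months for three of them).

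The trial is single-arm, so this is its only internal comparison bearing on whether following the recommendation helps. A favourable result could come from the classification rule or from case selection.

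**Working it through.** **The plan's own figure.** The only sample size in the documents belongs to the primary test (section 10.1: median 8 to 12 months, two-sided alpha 0.10, power 0.80, 18 months' accrual plus 6 months' follow-up). It reproduces:

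- Events: (1.645 + 0.842)² / (ln 1.5)² = 37.6.
- P(event) under the 12-month median, with λ = ln 2/12 = 0.0578: 1 − (e^(−6λ) − e^(−24λ))/(18λ) = 0.560.
- N = 37.6/0.560 = 67.1. The one-sample log-rank form with null and alternative variances gives 65.3, so 66.
- 66/0.90 = 73.3, so 74.

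Nothing comparable is stated for the concordance test.

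**How many labels can flip.** Assume median PFS 8 months in everyone (λ = ln 2/8 = 0.0866) and a drug start uniform over 0–1 month after the report. Then P(event before start) = 1 − (1 − e^(−λ))/λ = 0.042.

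- 10% planned discordant: 74 × 0.90 × 0.042 = 2.8 patients could move into a group planned at 7.4.
- 20% planned discordant: 74 × 0.80 × 0.042 = 2.5 patients could move into a group planned at 14.8.

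The numbers are small, but each is a very early event placed in a small group.

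**Simulation with no treatment effect.** Two-group log-rank, n = 74, exponential PFS with median 8 months, 18 + 6 months. A false benefit is z beyond 1.96 in favour of concordance. Pre-start events count as discordant. A stated share of events is recorded when it occurs and the rest at the next 3-monthly scan. The delay, the discordant share and the early-recording share are assumptions.

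| Planned discordant | Quarter recorded early | Half | All | No timing bias | 1-month landmark |
|---|---|---|---|---|---|
| 10% | about 10% | about 17% | about 32% | about 5–6% | about 5% |
| 20% | about 6% | about 10% | about 17% | about 4% | about 4% |

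The comparator is the no-timing-bias column, not the nominal 2.5%. With so few discordant patients the log-rank approximation is skewed even when nothing is wrong (5.2% and 3.6% in runs of 20,000 trials).

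**Dependence on the unstated rule.** A second set used N = 99, 75% intended concordant, exponentially distributed delay and no effect. Event dates are continuous except in the scan-only row. The unbiased rate here is 2.9%.

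| Handling of pre-start events | Mean delay | Median HR | False benefit |
|---|---|---|---|
| Counted as discordant | 0.25 month | 0.88 | 7.5% |
| Counted as discordant | 0.5 month | 0.79 | 15.5% |
| Counted as discordant | 1 month | 0.65 | 35% |
| Dropped from the concordant group only | 1 month | 0.88 | 7.2% |
| Dropped from both groups | 1 month | 1.00 | 3.5% |
| Counted as discordant, all events at 3-monthly scans | 0.5 month | 0.99 | 3.0% |
| Counted as discordant, all events at 3-monthly scans | 1 month | 0.93 | 4.6% |

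**Confounding alone.** With no delay, oncologist choice depending on prognosis (log-odds ±0.5 per SD) and log-hazard 0.5 per SD (assumptions), the null HR is 0.80 if better-prognosis patients follow the recommendation and 1.24 if worse-prognosis patients do.

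**The case against.** A reader might infer that the test, as written, necessarily favours concordance. The documents do not support that.

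- **Patients given nothing.** Section 10.2.2 defines the comparator by a different treatment actually given, so a patient who dies untreated after the report belongs to neither group on that wording. The bias needs pre-start events to be counted as discordant, or dropped from the concordant group alone. Patients on a non-matching bridging drug are the realistic route, and the documents do not say how many there will be. A patient already bridged on a matching class has no delay. This stands and makes the finding conditional, but the plan contains no rule that rules the bias out.
- **Scan timing.** Section 8 recommends restaging every 3 months (± 1 month). If events surface only at scans, the timing bias nearly disappears, so the 32% and 17% figures are upper cases. This stands in part: PFS includes death, and unscheduled imaging can detect progression earlier.
- **Direction of confounding.** It cannot be presumed to favour concordance. This stands.
- **Heavy modelling.** A Cox model stratified by four recommended groups with several covariates is tempting, but about 7–15 discordant patients cannot support it. This stands.
- **Stakes.** This is a secondary comparison in a phase II trial, with no alpha assigned and no decision tied to it. That limits the consequence but does not remove the defect.

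**Conclusion.** The concern holds in conditional form. Groups are set by treatment received after time zero, no start window or rule for pre-start events exists, and the test is unadjusted on oncologist-chosen treatment. It can therefore show a benefit of concordance that is not there.

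For 74 patients and starts within a month of the report, the false-benefit rate rises from a baseline of about 5–6% to between 10% and 32% at 10% discordant, and from about 4% to between 6% and 17% at 20% discordant. These ranges rest on the assumed delay, discordant share and early-recording share, and on counting pre-start events as discordant. With scan-only detection or symmetric exclusion the timing component is negligible. Confounding remains in either case, with unknown sign. This should be corrected, but it does not threaten the trial's primary result or the 66/74 sample size.

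**What to change.** In section 10.2.2 (PFS):

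1. Classify concordance by the therapy started by a fixed landmark after report delivery (e.g. 1 month). Compare PFS from the landmark among patients still event-free. In the simulations this returns the false-benefit rate to baseline (about 4–5%).
2. Label the result an exploratory, non-causal association, because the landmark removes the timing bias but not confounding by choice.
3. Allow at most a parsimonious adjustment (e.g. ECOG) as a sensitivity analysis, and only if the discordant group is large enough.
4. Reconcile the bridging allowance in section 6.1 with the censoring rule in section 9.1.3. Read literally, that rule could censor a patient on moving from bridging to the recommended therapy.

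The cost is SAP wording. Patients with events before the landmark leave this secondary analysis: at most about 74 × (1 − e^(−0.0866)) = 6 of 74 at 1 month if every event is recorded as it occurs, and fewer if progression is found at scans. Patients who start the recommended drug after the landmark stay in the discordant group, so the landmark should be chosen with the expected start delay in mind. The primary analysis and the 66/74 sample size do not change.
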